11.12. Reporting and Publication, Including Archiving

Essential documents are those documents that individually and collectively permit evaluation of the study and quality of the data produced. After completion of the study (end of study defined as the date of the last visit of the last subject), all documents and data relating to the study will be kept in an orderly manner by the Investigator in a secure study file. This file will be available for

inspection by the Sponsor or its representatives. Essential documents should be retained for 2 years after the final marketing approval in a region, for at least 2 years since the discontinuation of clinical development of the investigational product, or according to local requirements, whichever is longer. It is the responsibility of the Sponsor to inform the study center when these documents no longer need to be retained. The Investigator must contact the Sponsor before destroying any study-related documentation. In addition, all subject medical records and other source documentation will be kept for the maximum time permitted by the hospital, institution, or medical practice.

The Sponsor must review and approve any results of the study or abstracts for professional meetings prepared by the Investigator(s). Published data must not compromise the objectives of the study. Data from individual study centers in multicenter studies must not be published separately.

13. APPENDICES

APPENDIX A. SCHEDULE OF EVENTS FOR SCREENING AND CYCLES 1 & 2

Study Period	Screening ^a	Pre-Treatment (Baseline)	Treatment Period										Treatment Period									
			Cycle 1 ^q										Cycle 2 ^q									
Cycle	D-28 to D-1	D0 to D1	D1	D2	D3 ^t	D5 ^t	D8	D15	D16	D22	D28 ^p	D1 ^p	D2	D3 ^t	D5 ^t	D8	D15	D16	D22	D28 ^p		
Day					+1	+1	±1	±3			±3	+3	+1		+1	+1	±1	±3		±3	+3	
Visit Window (days)																						
Informed consent form	X																					
Inclusion/exclusion criteria	X																					
Hepatitis B and C testing	X																					
Medical history	X																					
ECOG PS	X	X											X	X								X
Physical examination ^b	X	X					X	X		X	X	X					X	X		X	X	
Slit lamp exam and visual acuity ^s	X												X	X								X
Pregnancy test ^c	X	X											X	X								X
Vital sign measurement and oxygen saturation ^d	X	X	X	X			X	X	X	X	X	X					X	X	X	X	X	
12-lead ECG ^e	X	X	X	X			X	X	X		X	X	X				X	X	X		X	
Hematology (Table 8)	X	X					X	X		X	X	X					X	X		X	X	
Serum chemistry (fasting) ^g (Table 9)	X	X					X	X		X	X	X					X	X		X	X	
HgbA1c ^r		X																				
Coagulation parameters ^g (Table 10)	X												X	X								X
Urinalysis ^h	X												X	X								X
PSA ⁱ		X											X	X								X
Tumor markers ^j	X												X	X								X
Tumor imaging and measurements ^k	X																					
PK ^l																						

Study Period	Screening ^a	Pre-Treatment (Baseline)	Treatment Period										Treatment Period										
			Cycle 1 ^q										Cycle 2 ^q										
Cycle	D-28 to D-1	D0 to D1	D1	D2	D3 ^t	D5 ^t	D8	D15	D16	D22	D28 ^p	D1 ^p	D2	D3 ^t	D5 ^t	D8	D15	D16	D22	D28 ^p			
Day					+1	+1	±1	±3		±3	+3	+1		+1	+1	±1	±3		±3	+3			
Visit Window (days)					X	X	X	X	X	X		X	X	X	X	X	X	X	X				
Part 1					X	X	X	X	X	X		X	X	X	X	X	X	X	X				
Part 2					X	X		X	X														
Pharmacodynamic & biological studies ^m					X	X		X	X	X		X	X										X
Circulating tumor DNA ⁿ					X								X	X									X
Tumor biopsy or submission of tumor specimen ^f			X																				X
KZR-261 treatment ^o					X			X	X				X						X	X			
Concomitant medications			X		X	X		X	X	X	X	X	X	X	X	X		X	X	X	X	X	
AE and SAEs			X																				

AEs collected through 30 days after last KZR-261 dose.

Abbreviations: AE=adverse event; aPTT=activated partial thromboplastin time; β -hCG= β -human chorionic gonadotropin; CA=cancer antigen; CEA=carcinoembryonic antigen; CT=computed tomography; DNA=deoxyribonucleic acid; ECG=electrocardiogram; ECOG PS=Eastern Cooperative Oncology Group Performance Status; EOT=End of Treatment; INR=internal normalized ratio; mCRPC=metastatic castration-resistant prostate cancer; MRI=magnetic resonance imaging; PBMC=peripheral blood mononuclear cell; PCWG3= Prostate Cancer Working Group 3; PD= progressive disease; PK=pharmacokinetics; PSA=prostate-specific antigen; PT=prothrombin time; PTT=partial thromboplastin time; RECIST=Response Evaluation Criteria in Solid Tumors; RNA=ribonucleic acid; SAE=serious adverse event; WOCBP=woman of childbearing potential

- ^a All Screening procedures must be performed prior to the Day 0 or Day 1 visit. Eligibility for this study should be assessed only after signing of informed consent.
- ^b A complete physical examination including measurement of body weight will be conducted at Screening and Baseline. Height will be measured at the Screening visit only. An abbreviated physical examination including measurement of body weight will be conducted at all other study visits indicated. Subjects with skin, subcutaneous, or lymph node metastases may also have tumor evaluations (including measurements, with a ruler or calipers) by means of physical examination. Patients will be asked at each visit about mouth dryness and salivary gland pain and sensitivity, and urinary and ejaculation issues.
- ^c For WOCBP, a negative serum β -hCG pregnancy test is required at Screening and a negative pregnancy test, serum or urine, at all other visits indicated. The Screening visit test should be performed within 2 weeks prior to treatment and in closer proximity to treatment start date if required by local/institutional regulations. A positive urine pregnancy test result should be confirmed by a serum pregnancy test. Pregnancy testing may occur more frequently if required by local/institutional regulations.
- ^d Vital signs and oxygen saturation will be measured at all visits except Days 3 and 5. Blood pressure and pulse should be measured after the subject has had at least 5 minutes of rest in the seated position. If blood pressure is elevated on the first measurement at Screening or Baseline, it should be repeated after an additional 5 minutes of rest. It is recommended that blood pressure be obtained from the same arm at each assessment.

- c When performed at the same time point, vital sign measurements should be performed per institutional guidelines, preferably prior to ECGs. A 12-lead ECG is performed 10 minutes after the subject has been in the supine position. ECGs will be performed on Days 1 and 15 of Cycles 1 and 2 pre-treatment, 15 minutes after the start of the infusion, at the end of the infusion, and 5 and 30 minutes, and 2, 4, 6, and 24 hours (Day 2 and Day 16) post-infusion. Additional ECGs will be performed on Day 8, 30 minutes prior to infusion, and 5 and 15 minutes and 1-hour post-infusion. ECG time points during the infusion, at the end of the infusion, and \leq 1 hour post-infusion have a \pm 2 minute window. ECG time points $>$ 1 hour post-infusion have a \pm 5 minute window; the 24-hour ECG has a \pm 60 minute window.
- f Tumor biopsies (fresh [preferred] or archived) will be requested pre-treatment. Although a fresh sample is preferred, submission of an adequate tumor specimen (paraffin block) collected within one year before the subject's first dose of KZR-261 will be acceptable for subjects where a fresh sample cannot be obtained. If a paraffin block is not available, a minimum of 10 and up to 20 5- μ m unstained slides should be provided. For any subject who provided a tumor sample pre-treatment, an additional biopsy of accessible tumor will be requested at either the end of Cycle 2 (Days 21-28 of Cycle 2) or at PD, whichever comes first. Pre-treatment tumor biopsies (fresh only) will be required for subjects enrolled in the All-Tumors expansion cohort (exceptions to this requirement may be considered after discussion with the Medical Monitor); an additional biopsy of accessible tumor tissue will be required at either the end of Cycle 2 (Days 21-28 of Cycle 2) or at PD, whichever comes first. Blood samples for coagulation parameter tests must be collected within 24 hours prior to all biopsy procedures.
- g Blood samples for serum chemistry tests must be collected with subject in a fasting state (ie, no food or caloric drinks for at least 6 hours before testing, or overnight). For coagulation parameter tests, either PT or INR may be measured, and either PTT or aPTT, depending on institutional standards. Blood samples for coagulation parameter tests must be collected within 24 hours prior to all biopsy procedures. It is recommended that the smallest appropriate sampling tubes be used for sample collection to curtail blood loss due to phlebotomy.
- h Urinalysis dipstick testing is acceptable.
- i Only subjects with mCRPC.
- j If tumor markers in blood (eg, PSA, CA-125, CEA, CA-15.3, CA-19.9) are known to be elevated, they should be measured.
- k All subjects must have Baseline imaging (CT scan of chest/abdomen/pelvis or MRI, as indicated) within 28 days prior to first dose of study treatment. Imaging should be repeated prior to Cycle 3 (ie, end of Cycle 2). There is a 7-day window around imaging procedures to allow time for result availability prior to the next cycle. If an imaging procedure must be scheduled to occur outside the 7-day window allowance, this should be discussed with the Medical Monitor for approval prior to the procedure. Response assessments will be conducted in accordance with RECIST 1.1 criteria. Subjects with mCRPC will be assessed per PCWG3 guidelines. All subjects with mCRPC will have bone scans at the same time points as the imaging procedures. Subjects with skin, subcutaneous, or lymph node metastases may also have tumor evaluations (including measurements, with a ruler or calipers) by means of physical examination.
- l Plasma PK samples will be collected during Part 1 on Days 1 and 15 of Cycles 1 and 2 pre-treatment, 15 minutes post-start of infusion, end of infusion, 5 minutes, 15 minutes, 30 minutes, 1 hour, 2 hours, 4 hours, 6 hours, and 24 hours (ie, Day 2 and Day 16) post-infusion. An additional plasma sample will be obtained in Cycles 1 and 2 at 48 hours (Day 3) and 96 hours (Day 5) post-infusion and on Day 8 at pre-treatment (30 minutes prior to infusion), 15 minutes and 1 hour after completion of the infusion. Plasma PK samples will be collected during Parts 2A and 2B on Day 1 of Cycle 1 at the end of infusion and 24 hours post-start of infusion (Day 2). An additional plasma sample will be obtained on Days 8 and 15 prior to infusion and Day 15 at the end of infusion. Windows for PK sampling are provided in the laboratory manual.
- m Whole blood samples will be collected for pharmacodynamic studies Cycle 1 Day 1 pre-treatment, 6 hours post-dose, 24 hours post-dose (Day 2), Cycle 1 Day 8 pre-treatment and Cycle 1 Day 15 pre-treatment, 6 hours post-dose, 24 hours post-dose (Day 16), and Cycle 2 Day 1 pre-treatment in a [REDACTED]

tube for RNAseq, in sodium heparin to be shipped to central laboratory for PBMC processing, and in sodium heparin processed onsite to plasma samples (as described in the laboratory manual). Samples will be collected on Cycle 1 Day 28 if treatment is halted and not proceeding to Cycle 2.

- ⁿ Whole blood will be collected in a [REDACTED] tube and shipped to the central laboratory for processing to plasma samples (for circulating tumor DNA testing) and cell pellet (cellular genomic DNA) pre-treatment Day 1 of Cycle 1, pre-treatment Day 1 Cycle 2, or at time of disease progression.
- ^o Subjects should remain at the study site for 6 hours following study treatment administration for observation for the first cycle, first dose (Cycle 1 Day 1) and for 2 hours for the rest of Cycle 1 dosing (Cycle 1 Days 8 and 15). For Cycle 2, subjects will be under observation for 1 hour following study treatment administration. For Cycle 3 and beyond, there will be no required monitoring following study treatment administration.
- ^p Day 28 assessments of the prior cycle may be combined with Day 1 of the next cycle. Whenever possible, these evaluations should be referred to as the End of Cycle evaluation (for the earlier cycle) as opposed to the beginning of cycle evaluation for the subsequent cycle.
- ^q For subjects who discontinue study treatment during or after Cycles 1 or 2, see EOT evaluations in [Appendix B](#). Subsequent to discontinuation of study treatment, subjects will have an EOT visit as soon as possible following their last KZR-261 dose and prior to initiation of follow-on anticancer therapy. Safety follow-up by telephone will occur approximately 30 days following their last KZR-261 dose. Subjects who discontinue study treatment for reasons other than PD will be contacted by telephone approximately every 90 days for 12 months after last study treatment for evidence of PD, collection of information about subsequent anti-tumor therapy, and assessment of survival status. Subjects who discontinue study treatment for PD will be contacted by telephone approximately every 90 days for 12 months after last study treatment for assessment of survival status.
- ^r HgbA1c to be measured at pre-treatment (baseline).
- ^s Subjects will have monitoring for cataracts at Screening, at the end of Cycle 1 prior to the start of Cycle 2, and at the end of Cycle 2 prior to Cycle 3.
- ^t Day 3 and Day 5 visits are for Part 1 only.

APPENDIX B. SCHEDULE OF EVENTS FOR CYCLE 3+

Study Period	Treatment Period					EOT/EW (as soon as possible after last dose of study treatment) ^l	Safety F/U 30 days after last dose of study treatment ^l	Long-Term F/U 12 months after last dose of study treatment ^m
	D1 ^k	D8	D15	D22	D28 ^k			
Day								
Visit Window (days)	±3	±1	±3	±3	±3			
ECOG PS	X				X	X		
Physical examination ^a	X				X	X		
Slit lamp exam and visual acuity ^b	X				X	X		
Pregnancy test ^c	X				X			
Vital sign measurement and oxygen saturation ^d	X	X	X	X	X	X		
12-lead ECG ^e	X	X ^e	X ^e		X	X		
Hematology (Table 8)	X	X	X	X	X	X		
Serum chemistry (fasting) ^f (Table 9)	X	X	X	X	X	X		
HgbA1c ^g	X				X			
Coagulation parameters ^f (Table 10)	X				X	X		
Urinalysis ^g	X				X	X		
PSA ^h	X				X			
Tumor markers ⁱ	X				X			
Tumor imaging and measurements ^j					X	X		
Circulating tumor DNA ⁿ	X				X	X		
KZR-261 Treatment	X	X	X					
Concomitant medications	Concomitant medications through 30 days after the last dose.					X		
AE and SAEs	AEs collected through 30 days after last KZR-261 dose.					X		
Disease/survival status						X		X

Abbreviations: AE=adverse event; aPTT=activated partial thromboplastin time; β-hCG=β-human chorionic gonadotropin; CA=cancer antigen; CEA=carcinoembryonic antigen; ECG=electrocardiogram; ECOG PS=Eastern Cooperative Oncology Group Performance Status; EOT=End of Treatment; EW=Early Withdrawal; F/U=Follow-Up; INR=internal normalized ratio; mCRPC=metastatic castration-resistant prostate cancer; PD=progressive disease;

PSA=prostate-specific antigen; PT=prothrombin time; PTT=partial thromboplastin time; RECIST=Response Evaluation Criteria in Solid Tumors; SAE=serious adverse event; WOCBP=woman of childbearing potential

- ^a For Cycles 3+, an abbreviated physical examination including weight, is only required prior to the start of each cycle (Day 1) and at the EOT visit. Subjects with skin, subcutaneous, or lymph node metastases may also have tumor evaluations (including measurements, with a ruler or calipers) by means of physical examination. Patients will be asked at each visit about mouth dryness and salivary gland pain and sensitivity, and urinary and ejaculation issues.
- ^b Subjects will have monitoring for cataracts at Cycle 4 Day 1 ±3 days, Cycle 6 Day 1 ±3 days. Slit lamp and visual acuity examinations should be conducted at EOT.
- ^c For WOCBP, a negative serum or urine pregnancy test, whichever is preferred, is required at all visits indicated. A positive urine pregnancy test result should be confirmed by a serum pregnancy test. Pregnancy testing may occur more frequently if required by local/institutional regulations.
- ^d Vital signs and oxygen saturation will be measured at all visits. Blood pressure and pulse should be measured after the subject has had at least 5 minutes of rest in the seated position. If blood pressure is elevated on the first measurement at Screening or Baseline, it should be repeated after an additional 5 minutes of rest. It is recommended that blood pressure be obtained from the same arm at each assessment.
- ^e When performed at the same time point, vital sign measurements should be performed per institutional guidelines, preferably prior to ECGs. A 12-lead ECG is performed 10 minutes after the subject has been in the supine position. ECGs will be performed on Day 1 pre-treatment and at the end of infusion for all cycles. For Cycle 4 only, ECGs will be performed on Days 1 and 15 at pre-treatment, 15 minutes after the start of the infusion, at the end of the infusion, and 5 and 30 minutes, and 2, 4, and 6 hours post-infusion. Additional ECGs for Cycle 4 only will be performed on Day 8, 30 minutes prior to infusion, and 5 and 15 minutes and 1 hour post-infusion. ECG time points during the infusion, at the end of the infusion, and ≤1 hour post-infusion have a ±2 minute window. ECG time points >1 hour post-infusion have a ±5 minute window. ECG time points >1 hour post-infusion have a ±5 minute window.
- ^f Blood samples for serum chemistry tests must be collected with subject in a fasting state (ie, no food or caloric drinks for at least 6 hours before testing, or overnight). For coagulation parameter tests, either PT or INR may be measured, and either PTT or aPTT, depending on institutional standards. It is recommended that the smallest appropriate sampling tubes be used for sample collection to curtail blood loss due to phlebotomy.
- ^g Urinalysis dipstick testing is acceptable.
- ^h Only subjects with mCRPC.
- ⁱ If tumor markers in blood (eg, PSA, CA-125, CEA, CA-15.3, CA-19.9) are known to be elevated, they should be measured.
- ^j Imaging should be repeated prior to Cycle 3, prior to Cycle 5 (ie, end of Cycle 4) and every 2 cycles thereafter (ie, end of Cycles 4, 6, 8 etc.). There is a 7-day window around imaging procedures to allow time for result availability prior to the next cycle. If an imaging procedure must be scheduled to occur outside the 7-day window allowance, this should be discussed with the Medical Monitor for approval prior to the procedure. Imaging should be repeated at EOT if the last response assessment was >4 weeks prior. Tumors will be measured according to RECIST v1.1. Subjects with mCRPC will be assessed per PCWG3 guidelines. All subjects with mCRPC will have bone scans at the same time points as the imaging procedures. Subjects with skin, subcutaneous, or lymph node metastases may also have tumor evaluations (including measurements, with a ruler or calipers) by means of physical examination.
- ^k Day 28 assessments of the prior cycle may be combined with Day 1 of the next cycle. Whenever possible, these evaluations should be referred to as the End of Cycle evaluation (for the earlier cycle) as opposed to the beginning of cycle evaluation for the subsequent cycle.
- ^l Subsequent to discontinuation of study treatment, subjects will have an EOT visit as soon as possible following their last KZR-261 dose and prior to initiation of follow-on anticancer therapy. Safety follow-up by telephone will occur approximately 30 days after the subject's last dose of study treatment. If AEs have not resolved at that time, additional safety follow-ups will occur approximately every 30 days until AE resolution or until, in the opinion of the Investigator, the event is stabilized or determined to be chronic.
If a subject attending a Day 28 or Day 1 visit meets criteria for EOT, the EOT visit assessments should be conducted instead of Day 28/Day 1 assessments.

- ^m Subjects who discontinue study treatment for reasons other than PD will be contacted by telephone approximately every 90 days for 12 months after last study treatment for evidence of PD, collection of information about subsequent anti-tumor therapy, and assessment of survival status. Subjects who discontinue study treatment for PD will be contacted by telephone approximately every 90 days for 12 months after last study treatment for assessment of survival status.
- ⁿ Whole blood will be collected in a [REDACTED] tube and shipped to the central laboratory for processing to plasma samples (for circulating tumor DNA testing) and cell pellet (cellular genomic DNA) pre-treatment Day 1 of Cycles 3-6. A circulating tumor DNA sample should be collected at EOT or at time of disease progression. This collection is not required for subjects who continue to receive treatment beyond Cycle 6.
- ^o HgbA1c to be measured on Day 28 every 3 cycles (ie, end of Cycles 3, 6, 9, etc.) or at Day 1 prior to treatment of the following cycles (ie, Day 1 of cycles 4, 7, 10, etc.).

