Subjects will receive KZR-261 for up to 6 cycles. Upon completion of Cycle 6, a subject who is deriving clinical benefit may continue treatment at the discretion of the Investigator and with agreement of the Medical Monitor. Study treatment will be discontinued at any time for unacceptable AEs, progressive disease, voluntary withdrawal by the subject, another discontinuation criterion is met, or study closure by the Sponsor (Section 8.1.2).

Following discontinuation of study treatment, subjects will complete an End of Treatment (EOT) visit as soon as possible after their last dose of study treatment (Section 8.3). Safety follow-up will be conducted by telephone 30 days after the subject's last dose of study treatment (Section 9.1.5). If AEs have not resolved at that time, additional safety follow ups will occur approximately every 30 days until resolution of AEs or until, in the opinion of the Investigator, the event is stabilized or determined to be chronic.

Subjects who discontinue study treatment for reasons other than progressive disease (PD) will be contacted by telephone approximately every 90 days for 12 months after last study treatment for evidence of PD, collection of information about subsequent anti-tumor therapy, and assessment of survival status. Subjects who discontinue study treatment for PD will be contacted by telephone approximately every 90 days for 12 months after last study treatment for assessment of survival status.

Safety will be assessed as described in [Section 2.2.1.1](#).

Anti-tumor activity will be assessed as described in [Section 2.2.2.1](#), with assessments of response conducted after every 2 treatment cycles.

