Cataract ≤Grade 2 or baseline; any other ocular toxicity ≤Grade 1 or baseline	No dose adjustment if within a cycle or for subsequent cycles unless slit-lamp examination reveals treatment-emergent progression of incidental, asymptomatic cataract that is considered at least possibly related to study drug. If progression occurred, reduce dose by one level.

Abbreviations: NCI CTCAE=National Cancer Institute Common Terminology Criteria for Adverse Events

Table 7: Dose Modifications for Other Toxicity

NCI CTCAE Grade	Dose Adjustment
≥Grade 3 with resolution to ≤Grade 2 or baseline within 1 week	Withhold dose until ≤Grade 1 or baseline, then: 
Resume KZR-261 at the same dose or reduce dose by one level if within a cycleBegin subsequent cycles at the same or reduced dose level
≥Grade 3 lasting ≥1 week	
Withhold dose until ≤Grade 1 or baselineReduce dose by one level if within a cycle, and begin subsequent cycles at a reduced dose level

Abbreviations: NCI CTCAE=National Cancer Institute Common Terminology Criteria for Adverse Events

Note:

- In the setting of Grade 2 toxicities not referenced above, including (but not limited to) nausea, vomiting, diarrhea, or fatigue that recur in successive cycles or are persistently debilitating in the opinion of the subject or Investigator, dose reduction by one level may be considered if within a cycle and for subsequent cycles and should be discussed with the Medical Monitor.

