Vital sign measurements should be performed per institutional guidelines, preferably prior to ECGs. A 12-lead ECG is performed 10 minutes after the subject has been in the supine position. The Investigator or qualified designate will review and indicate if the ECG is normal or abnormal, and if abnormal, whether clinically significant. Any medically significant changes from the Screening ECG will be recorded as an AE.

7.2.5. *Vital Sign Measurements and Oxygen Saturation*

Vital signs measurements (including systolic and diastolic blood pressure, pulse rate, respiration rate, and body temperature) and oxygen saturation will be collected at all study visits. Blood pressure and pulse should be collected after the subject has had at least 5 minutes of rest in the seated position. If blood pressure is elevated on the first measurement at Screening or Baseline, it should be repeated after an additional 5 minutes of rest. It is recommended that blood pressure is measured using the same arm at each assessment. When the time of vital signs measurement coincides with a blood sample collection, vital signs will be measured per institutional guidelines.

7.2.6. *Ocular Examination*

Slit lamp and visual acuity examinations will be conducted to monitor for cataracts and should be reviewed prior to administration of KZR-261 at the beginning of each cycle where an eye examination is required ([Appendix A](#) and [Appendix B](#)). Any medically significant changes from the Screening evaluation will be recorded as an AE.

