7.2.10. Response Assessments

Assessments of response and progression will occur in accordance with RECIST v1.1 ([Eisenhauer et al., 2009](#)) at timepoints shown in the Schedule of Events ([Appendix A](#) and [Appendix B](#)). Subjects with mCRPC will be assessed per PCWG3 guidelines ([Scher et al., 2016](#)).

All subjects must have contrast-enhanced imaging studies of chest, abdomen, and pelvis as well as other areas of suspected disease within 28 days prior to their first dose of study treatment. The preferred imaging modality is contrast-enhanced computed tomography (CT). In subjects for whom IV contrast for CT is contraindicated, perform contrast-enhanced magnetic resonance imaging (MRI) scanning of the aforementioned anatomic regions with non-contrast enhanced CT of the chest. Subjects known to have fluorodeoxyglucose (FDG)-avid tumors are required to undergo positron emission tomography (PET) scanning along with the CT scan at Screening. Subjects whose tumors demonstrate FDG update at Screening should undergo follow-up PET scanning post-Cycle 6, post-Cycle 12, and every 6 cycles thereafter (see below). Subjects with skin, subcutaneous or lymph node metastases may also have evaluations of measurable lesions (including measurements, with a ruler or calipers) by means of physical examination.

Subjects with mCRPC must have a baseline PSA and bone scan in addition to the aforementioned imaging studies. (Note: A rising PSA as the sole indicator of disease activity will not lead to a determination of disease progression.) On-treatment bone scans will be performed at the same time points as CT/MRI scans. As a rule, the same imaging modality (ie, CT or MRI or combined CT/PET scans) should be used for all scheduled tumor assessments and measurements.

Imaging studies should be repeated prior to Cycle 3 (ie, end of Cycle 2) and every 2 cycles thereafter (ie, end of Cycles 4, 6, 8, etc). There is a 7-day window for imaging procedures to allow time for availability of results prior to the next cycle. If an imaging procedure must be scheduled to occur outside the 7-day window, this should be discussed with the Medical Monitor for approval prior to the procedure.

Response assessments, including imaging studies, are to be performed at the EOT visit, if PD has not already been established and the last response assessment was conducted >4 weeks prior to EOT.

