b Subjects will have monitoring for cataracts at Cycle 4 Day 1 ±3 days, Cycle 6 Day 1 ±3 days. Slit lamp and visual acuity examinations should be conducted at EOT.

c For WOCBP, a negative serum or urine pregnancy test, whichever is preferred, is required at all visits indicated. A positive urine pregnancy test result should be confirmed by a serum pregnancy test. Pregnancy testing may occur more frequently if required by local/institutional regulations.

d Vital signs and oxygen saturation will be measured at all visits. Blood pressure and pulse should be measured after the subject has had at least 5 minutes of rest in the seated position. If blood pressure is elevated on the first measurement at Screening or Baseline, it should be repeated after an additional 5 minutes of rest. It is recommended that blood pressure be obtained from the same arm at each assessment.

e When performed at the same time point, vital sign measurements should be performed per institutional guidelines, preferably prior to ECGs. A 12-lead ECG is performed 10 minutes after the subject has been in the supine position. ECGs will be performed on Day 1 pre-treatment and at the end of infusion for all cycles. For Cycle 4 only, ECGs will be performed on Days 1 and 15 at pre-treatment, 15 minutes after the start of the infusion, at the end of the infusion, and 5 and 30 minutes, and 2, 4, and 6 hours post-infusion. Additional ECGs for Cycle 4 only will be performed on Day 8, 30 minutes prior to infusion, and 5 and 15 minutes and 1 hour post-infusion. ECG time points during the infusion, at the end of the infusion, and ≤1 hour post-infusion have a ±2 minute window. ECG time points >1 hour post-infusion have a ±5 minute window. ECG time points >1 hour post-infusion have a ±5 minute window.

f Blood samples for serum chemistry tests must be collected with subject in a fasting state (ie, no food or caloric drinks for at least 6 hours before testing, or overnight). For coagulation parameter tests, either PT or INR may be measured, and either PTT or aPTT, depending on institutional standards. It is recommended that the smallest appropriate sampling tubes be used for sample collection to curtail blood loss due to phlebotomy.

g Urinalysis dipstick testing is acceptable.

h Only subjects with mCRPC.

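### If Appendix B footnote b governs, no slit-lamp exam is scheduled between Cycle 6 Day 1 and end of treatment, so the Table 6 cataract dose reduction has no scheduled trigger in subjects who continue

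*Protocol*

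**What the plan says.** **Schedule.** In Appendix B of the Protocol, the slit-lamp and visual acuity row for Cycle 3+ is marked at Day 1, Day 28 and EOT and carries footnote b. The footnote reads "Subjects will have monitoring for cataracts at Cycle 4 Day 1", then adds Cycle 6 Day 1 (each with a window of plus or minus 3 days) and EOT. The SAP's Appendix B repeats it, including "Slit lamp and visual acuity examinations should be conducted at EOT". Appendix A, footnote s, covers the earlier period: Screening, end of Cycle 1 and end of Cycle 2.

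**Section 7.2.6 (Ocular Examination).** Timing is left to the appendices. Results are to be reviewed before dosing "at the beginning of each cycle where an eye examination is required".

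**Duration.** Under Protocol Section 3.1, a subject who benefits "may continue treatment at the discretion of the Investigator and with agreement of the Medical Monitor" after Cycle 6. No maximum is given. Section 7.2.10 provides for long treatment: subjects with FDG-avid tumors "should undergo follow-up PET scanning post-Cycle 6, post-Cycle 12, and every 6 cycles thereafter".

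**Dose rule.** Table 6 (Section 6.1.4.2) requires no adjustment for low-grade cataract "unless slit-lamp examination reveals treatment-emergent progression of incidental, asymptomatic cataract that is considered at least possibly related to study drug". In that case the dose is reduced by one level. Section 6.1.4 allows reductions from Cycle 2 on in Part 1 and in every cycle in Part 2, so the rule does not lapse at Cycle 6.

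**The concern.** The grid and its footnote disagree, and neither says which applies once a subject goes past Cycle 6. If the footnote governs, the last scheduled lens exam on treatment is at Cycle 6 Day 1. The next is at EOT, which Section 8.3.1 places after permanent discontinuation, when a dose reduction is no longer possible.

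The Table 6 rule rests on a slit-lamp finding in a subject without symptoms, so routine adverse-event questioning would not be expected to bring it out. The subjects affected are those deriving benefit, for whom lowering the dose is of more use than stopping. They could remain on full dose with a progressing cataract that the protocol says should lead to a reduction. If some sites follow the grid and others the footnote, monitoring would also differ between sites.

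**Working it through.** The plan gives no figure to reproduce. The check compares the two readings and counts exams, weeks and doses.

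**Which reading is more natural**

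- Other Appendix B footnotes narrow their grid rows. Imaging is marked at every Day 28, but footnote j makes it every two cycles. HgbA1c is marked at Day 1 and Day 28, but footnote o says "HgbA1c to be measured on Day 28 every 3 cycles".
- Those footnotes also say what happens later. Footnotes j and o run past Cycle 6 with an open-ended series. Footnote n ends circulating tumor DNA sampling explicitly: "This collection is not required for subjects who continue to receive treatment beyond Cycle 6". Footnote b does neither.
- If the grid applied to every cycle, naming Cycles 4 and 6 would serve no purpose. The wording of Section 7.2.6 also suggests that not every cycle has an eye exam.

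The footnote reading is therefore more likely, but the text does not compel it.

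**Inputs**

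- 28-day cycles, doses on Days 1, 8 and 15 (Protocol Section 3.1).
- Windows of plus or minus 3 days at Day 1 and Day 15 (Appendix B).
- Assumed: final cycle N, last dose on Day 15 of that cycle, no delays.

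**Exams up to Cycle 6**

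Day 1 of cycle c is study day 1 + 28 × (c − 1). Cycle 4 Day 1 is day 85 and Cycle 6 Day 1 is day 141. On-treatment exams fall at about weeks 4, 8, 12 and 20, at intervals of 4, 4 and 8 weeks. The 8-week interval contains the 6 doses of Cycles 4 and 5.

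**From Cycle 6 Day 1 to the last dose (footnote reading)**

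- Weeks = 4 × (N − 6) + 2
- Doses, counting Cycle 6 = 3 × (N − 5)

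**Exams after Cycle 6 Day 1 and before EOT**

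- Footnote reading: 0
- Grid reading, with Day 28 combined with the next Day 1 and EOT replacing the last Day 28: N − 6

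| N | Weeks to last dose | Doses | Exams, footnote | Exams, grid |
|---|---|---|---|---|
| 6 | 4 × 0 + 2 = 2 | 3 × 1 = 3 | 0 | 0 |
| 7 | 4 × 1 + 2 = 6 | 3 × 2 = 6 | 0 | 1 |
| 8 | 4 × 2 + 2 = 10 | 3 × 3 = 9 | 0 | 2 |
| 12 | 4 × 6 + 2 = 26 | 3 × 7 = 21 | 0 | 6 |

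**Could visit windows explain the excess?**

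With 3 days either way at both ends:

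- Cycle 4 Day 1 to Cycle 6 Day 1: 56 ± 6 = 50 to 62 days.
- Cycle 6 Day 1 to Cycle 8 Day 15: 70 ± 6 = 64 to 76 days.

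The ranges do not overlap, so from 8 cycles on the gap exceeds anything the earlier schedule allows.

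**The case against.** The strongest reply is that the gap depends on a reading the text does not force. The grid has no upper limit, footnote b never says *only*, and elsewhere the appendix uses explicit limiting words when it means to restrict. On the literal grid, exams continue every cycle and Table 6 keeps its trigger. The Section 7.2.6 wording is weak evidence, since it also covers Cycle 1, whose only prior exam is at Screening. This stands as a reason to keep the finding conditional. It does not make the two instructions agree.

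It can also be said that a missing trigger and variation between sites cannot both apply in full. That is fair: which one follows depends on how sites read the schedule. Either calls for a correction.

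The planned six cycles are well covered: four on-treatment exams, then EOT, with only 2 weeks from the last on-treatment exam to the last dose. At 7 cycles the gap is 6 weeks, still inside the earlier 8-week maximum. The excess begins at 8 cycles, and the 12-cycle case is an illustration. All of this stands.

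Other controls exist: continuation needs Medical Monitor agreement, the Safety Review Committee keeps monitoring, unscheduled exams are not barred, and Table 6 would act on their findings. These soften the consequence, but none is a routine exam for change without symptoms.

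Finally, late risk is not shown. Protocol Section 1.2.3.1 reports monkey cataracts by Day 19/20 at 30 mg/m² or more, without correlation with total exposure. Those studies dosed for 4 weeks, however, and so do not exclude a later effect. The same section records that the cataracts progressed over a 2-week recovery period.

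**Conclusion.** The concern holds in its conditional form. If footnote b governs, no slit-lamp exam is scheduled on treatment after Cycle 6 Day 1, and the Table 6 reduction has no scheduled trigger for cataract progression that arises after that exam. Progression found at Cycle 6 Day 1 can still lower later doses.

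The unmonitored stretch exceeds the earlier 8-week maximum from 8 cycles on: by 2 weeks at 8 cycles (10 − 8) and by 18 weeks at 12 (26 − 8). These figures assume the stated durations and no dose delays. The documents do not say how many subjects will continue that long.

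This should be corrected because a site following the footnote as written would leave a stated dose-safety rule without the exam it needs. No efficacy estimate, escalation decision or interim rule is affected, and the EOT exam still captures the ocular endpoint.

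**What to change.** Amend footnote b in Appendix B of both the Protocol and the SAP to read: *Cycle 4 Day 1, Cycle 6 Day 1 and Day 1 of every second cycle thereafter while on treatment (Cycles 8, 10, 12, etc.), and at EOT.* This resolves the conflict with the grid and keeps the nominal maximum interval at 8 weeks. The 8-week figure simply carries forward the plan's own longest interval; the documents do not justify it as a required maximum.

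If the intention is to stop eye exams after Cycle 6, say so as footnote n does for circulating tumor DNA, and state how the Table 6 cataract rule is to be applied from then on.

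The cost is one sentence in each of two footnotes, plus non-invasive exams at Day 1 visits that already take place, in continuing subjects only. For even N the extra exams number (N − 6) / 2: one for 8 cycles and three for 12.
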